4.8 Monitoring Vaccine Safety in the First 15 Days

On the vaccination day and for the next 14 days post-vaccination (until day 15), all participants will be monitored daily by their parent(s) or legal guardian(s) and the information will be recorded using memory aids provided at the enrollment visit. Daily reactogenicity, including measurement of nighttime awakening, and unscheduled albuterol use and two validated questionnaires will be completed (c-ACT/ACT and PROSE). PROSE will be assessed at baseline (Day 1) and on Day 15.

In addition to the two questionnaires above, several predefined events that could occur after vaccine administration will also be recorded for 14 days after vaccination (through day 15). These will include fever (oral temperature $\geq 100.4^{\circ}$ F), asthma symptoms, and other respiratory and systemic symptoms. Medication receipt, new prescriptions for asthma medications, and any previously unscheduled healthcare utilization (medical office visits, ED visits, hospitalizations) will also be documented on the reaction form. To ensure compliance with the reaction assessment, parents will be called, emailed through REDCap, or receive text messages on Days 4, 8 and 15 by the study staff.

On the day of vaccination and during the first 14 days (until day 15) after vaccination, if the participant reports an increase in their symptoms and an increase in the need for medications for their asthma, the family will be instructed to contact the study staff, so medical records can later be collected, if needed. If at any point a study participant is experiencing symptoms of any asthma exacerbation, the participant or their parent will be instructed to contact their primary care provider (PCP) and inform study staff of this encounter.

4.9 Extended follow-up for days 16-43

After the initial 15-day follow up after vaccination, there will be an extended surveillance period for safety assessment from day 16 after vaccination for a total of 42 days (Day 43). This will be accomplished by a telephone call, text messaging, or email through the REDCap system to the parents of the participants, depending on their preference and their availability, at day 29 and at day 44 to determine the status of asthma control. On Day 29, participants will be queried about concomitant medications, unsolicited symptoms, serious adverse events, and medical services utilization. On day 44, participants will be queried about concomitant medications, unsolicited symptoms, serious adverse events, and medical services utilization. On day 44, participants will be queried about concomitant medications, unsolicited symptoms, serious adverse events, and medical services utilization. On day 44, participants will be queried about concomitant medications, unsolicited symptoms, serious adverse events, and medical services utilization. On day 44, participants will be queried about concomitant medications, unsolicited symptoms, serious adverse events, and medical services utilization.

During the extended follow up period, parents/legal guardian will be instructed to contact the study staff if the participant has an unscheduled medical visit for management of asthma symptoms or a new asthma medication prescribed.

4.10 Adverse Events and Serious Adverse Events

Adverse events (AEs) will be recorded on the memory aid and will include the need for new prescription or nonprescription medications for the control of asthma, an unscheduled healthcare provider visit or consultation within 42 days (until day 43) after vaccination, any other clinically significant event occurring at any point during the study period. Serious AEs (SAEs) will also be monitored through 42 days (until day 43) after vaccination and will include events that result in death, were life threatening, result in participant hospitalization or prolongation of existing hospitalization, result in persistent or significant disability or incapacity. Additionally, important medical events that may not have resulted in death, were not life threatening, or did not require hospitalization might be considered SAEs when, according to appropriate medical judgment, they jeopardize the patient or participant and require medical or surgical intervention to prevent one of the outcomes listed above. Medical records will be requested and reviewed to evaluate SAE and assess relatedness of SAEs to receipt of LAIV4 or IIV4

5 RISKS

5.1 Vaccines

All participants will receive the CDC Vaccine Information Statements (VIS) (https://www.cdc.gov/vaccines/hcp/vis/current-vis.html) before vaccination. With any medicine, including vaccines, there is a chance of reactions. These are usually mild and go away on their own, but serious reactions are also possible. Any medication or vaccine can cause a severe allergic reaction, including anaphylaxis. Such reactions from a vaccine are very rare, estimated at about 1 in a million doses, and would happen within a few minutes to a few hours after the vaccination. As with any medicine, there is a very small chance of a vaccine causing a serious injury or death.

5.1.1 Inactivated Influenza Vaccine (IIV)

ACIP routinely recommends IIV for children with asthma^{9,11,20} and risks after IIV would be expected to be no higher than those encountered through usual care. Most people who get a flu shot do not have any problems with it. Minor problems following a flu shot may include: soreness, redness, or swelling where the shot was given, hoarseness, sore, red or itchy eyes, cough, fever, aches, headache, itching, fatigue. If these problems occur, they usually begin soon after the shot and last 1 or 2 days. More serious problems following a flu shot can include the following: There may be a small increased risk of Guillain-Barré Syndrome (GBS) after inactivated flu vaccine. This risk has been estimated at 1 or 2 additional cases per million people vaccinated, primarily in adults. This is much lower than the risk of severe complications from flu, which can be prevented by flu vaccine. Problems could happen after any injected vaccine: People sometimes faint after a medical procedure, including vaccination. Sitting or lying down for about 15 minutes after vaccination can help prevent fainting and injuries caused by a fall. Some people get severe pain in the shoulder and have difficulty moving the arm where a shot was given.

5.1.2 Live, attenuated influenza vaccine (LAIV)

ACIP considers use of LAIV as a precaution for children aged \geq 5 years with asthma.¹ In addition to the usual risks as described in the VIS (https://www.cdc.gov/vaccines/hcp/vis/current-vis.html), children with asthma might experience higher rates of asthma exacerbations after LAIV than with IIV.^{9,11,20} Most people who get LAIV do not have any problems with it. Reactions to LAIV may resemble a very mild case of flu. Some of the most common symptoms that have been reported following LAIV in children and adolescents 2-17 years of age are runny nose, nasal congestion, sore throat, cough, fever, headache, muscle aches, wheezing, abdominal pain, vomiting, or diarrhea.¹⁰

There is also the potential risk of loss of confidentiality about the information obtained as part of this study (see section 9).

6 REPORTING OF ADVERSE EVENTS

Parent(s) or legal guardian(s) who at any time express any concern about symptoms or serious unsolicited events will be encouraged to follow up with their child's health care provider.

Serious adverse events (SAEs) will be reported to CDC and all participating IRBs according to institutional requirements.

If indicated, adverse events will be reported to CDC's Vaccine Adverse Event Reporting System (VAERS). The National Childhood Vaccine Injury Act requires healthcare providers to report:

- Any adverse event listed by the vaccine manufacturer as a contraindication to further doses of the vaccine; or
- Any adverse event listed in the VAERS Table of Reportable Events Following Vaccination (https://vaers.hhs.gov/docs/VAERS_Table_of_Reportable_Events_Following_Vaccination.pdf) [link accessed 5/2/2019) that occurs within the specified time period after vaccination.

In addition, CDC encourages reporting of any clinically significant adverse event that occurs in a patient following a vaccination, even if there is uncertainty regarding if a vaccine caused the event.

As noted in section 4.10, a SAE is an AE meeting one or more of the following criteria

- Life-threatening illness
- Death
- Hospitalization An event requiring inpatient hospitalization
- Prolongation of existing hospitalization
- Persistent or significant disability or incapacity

Additionally, important medical events that may not have resulted in death, were not life threatening, or did not require hospitalization might be considered SAEs when, according to appropriate medical judgment, they jeopardize the patient or participant and require medical or surgical intervention to prevent one of the outcomes listed above. These will be reported to the IRBs. SAEs will be assessed for relatedness to vaccine: related or not related.

Participants who report severe solicited AEs or SAEs or express any concern about symptoms, and/or unsolicited events will be encouraged to follow up with their pediatrician or primary care provider. Severe solicited or unsolicited adverse events are those that prevent daily activity and/or require a doctor's office visit or a missed day of school or daycare.

7 STUDY WITHDRAWAL AND DISCONTINUATION

Participants may voluntarily withdraw their consent for study participation at any time and for any reason, without penalty.

A participant may withdraw or be withdrawn from this study for any of the following reasons:

- Medical disease or condition, or any new clinical findings for which continued participation, in the opinion of the site principal investigator or appropriate sub-investigator, would compromise the safety of the participant, or would interfere with the participant's successful completion of this study, or would interfere with the evaluation of responses.
- As deemed necessary by the site principal investigator or appropriate sub-investigator for noncompliance or other reasons.
- Participant withdrawal of consent.
- Participant lost to follow-up.
- Termination of this study.
- New information becomes available that makes further participation unsafe.

Participants may withdraw their consent for study participation at any time and for any reason, without penalty.

7.1 Handling of Withdrawals

Participants who withdraw from the study before randomization will be replaced. Participants who withdraw from the study after randomization will not be replaced. Every attempt should be made to collect all data specified by the protocol relative to study vaccine received up to the time of withdrawal. Data collected before withdrawal will still be used for analysis.

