4.1 Recruitment

This is a prospective randomized, open label clinical trial in approximately 300 children aged 5-17 years, inclusive, with a physician diagnosis of persistent asthma. The study will be conducted at three sites: Vanderbilt University Medical Center (Lead site), Cincinnati Children's Hospital Medical Center (contributing site), and Duke University Medical Center (contributing site) during the 2018-2019 and 2019-2020 influenza seasons. Participants will be randomized 1:1 to receive either a single intranasal dose of LAIV4 or an intramuscular injection of IIV4, stratifying by asthma severity (mild vs. moderateto-severe) and by age group (5-11 years vs. 12-17 years of age). Vanderbilt will enroll approximately 100 participants, Cincinnati will enroll approximately 110 participants, and Duke will enroll approximately 90 participants. All sites will begin enrolling when study vaccines become available. Recruitment will occur at various clinics at the three study sites. At all sites, study participants will be compensated for the initial clinic visit at enrollment, and for each study visit follow-up (excluding reminder-only communications), as outlined in Section 4.3. A social security number will be requested for the parent, legal guardian, or child who receives monetary compensation for participating in this study. A child may participate in this study even if their parent or legal guardian chooses not to provide a social security number; however, the study will not be able to provide compensation to the parent, legal guardian, or child if a social security number is not provided.

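### Sections 7 and 7.1 provide for no data after an investigator withdraws a vaccinated child, although withdrawal ends only observation and the endpoint and SAE window runs to Day 43

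*Protocol*

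**What the plan says.** Protocol section 7 opens its list of grounds with "A participant may withdraw or be withdrawn from this study for any of the following reasons". Two of them rest on the investigator's judgement. One begins "Medical disease or condition, or any new clinical findings for which continued participation, in the opinion of the site principal investigator" and applies where staying in the study would compromise safety, completion or the evaluation of responses. The other reads "As deemed necessary by the site principal investigator or appropriate sub-investigator for noncompliance or other reasons". Withdrawal of consent and loss to follow-up are listed separately.

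Section 7.1 covers all withdrawals together: "Every attempt should be made to collect all data specified by the protocol relative to study vaccine received up to the time of withdrawal", then "Data collected before withdrawal will still be used for analysis", and "Participants who withdraw from the study after randomization will not be replaced". It does not separate withdrawal by the investigator from withdrawal of consent, and it describes no later contact or record review.

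Section 4.10 says "Serious AEs (SAEs) will also be monitored through 42 days (until day 43) after vaccination", without mentioning withdrawn children.

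Section 4.1 describes the intervention: "Participants will be randomized 1:1 to receive either a single intranasal dose of LAIV4 or an intramuscular injection of IIV4". Under section 4.7.3 a second dose, where a child needs one, is not a study procedure. Visits 2 to 6 (section 4.3) are remote reminders or contacts. Section 4.2 states that staff and families are not blinded.

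On the analysis side, PP43 is primary for the primary objective and requires study procedures to be completed through Day 43 (protocol 8.2, SAP 6.2). The ITT set keeps every randomized and vaccinated child. SAP 8.1 codes the endpoint 1 if a qualifying event occurred and 0 in every other case. The SAP has no missing-data rule, and its only sensitivity analysis is by vaccine received (SAP 10).

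**The concern.** In a trial with continuing treatment, investigator withdrawal can protect a child by stopping the treatment. Here the exposure is complete on Day 1, so withdrawal from Visit 2 onward removes only the watching. What stops is the set of contacts that feed the primary endpoint and the SAE listing.

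The information lost may not be random. A new medical condition can be related to the outcome, noncompliant families may have less well controlled asthma, and the person deciding knows which vaccine was given. Both analysis sets are exposed. PP43 drops the child, even one with an exacerbation already recorded. The ITT set keeps the child, but an event after withdrawal that no one records becomes a zero. If loss before the event were greater in LAIV4, both sets would move toward non-inferiority. SAEs after withdrawal could also be missing from exploratory objective 9. No analysis rule can restore an outcome that the site stopped asking about.

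**Working it through.** **1. The plan's own figure.** Protocol 8.1 and SAP 4.2 assume 12% in each arm, a 10-point margin, one-sided alpha of 0.05 and 135 evaluable children per arm.

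- Standard error = √(2 × 0.12 × 0.88 / 135) = 0.03955.
- Power = Φ(0.10/0.03955 − 1.645) = 81.1%, as stated.
- Enrolment: 135/0.90 = 150 per arm, 300 in total, as stated.

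The sample size is not in question.

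**2. Base error rate.** The decision rule in protocol 8.2.2 was enumerated exactly over two binomials with 135 per arm. It passes 81.2% of the time at 12% versus 12%. With true risks of 22% and 12%, exactly at the margin, it passes 5.2% of the time.

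**3. Withdrawal before the event, per-protocol view.** Let q be the fraction of children who would have an event but are withdrawn before it. They leave both numerator and denominator, so the observed risk is p(1 − q)/(1 − pq). The number analysed is held at 135 per arm. The values of q are assumptions; the documents give none.

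| q | LAIV4 risk from 22% | IIV4 risk from 12% |
|---|---|---|
| 5% | 21.1% | 11.5% |
| 10% | 20.2% | 10.9% |
| 20% | 18.4% | 9.8% |

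Chance of a false non-inferiority claim, from a base of 5.2%:

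| q | Loss in LAIV4 only | Equal q in both arms | Loss in IIV4 only |
|---|---|---|---|
| 5% | 7.6% | 6.1% | 4.1% |
| 10% | 10.9% | 7.2% | 3.2% |
| 20% | 21.1% | 10.1% | 1.8% |

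In LAIV4, with 135 × 0.22 = 29.7 expected events, these fractions are about 1.5, 3 and 6 children.

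**4. ITT view.** With 150 per arm and missed events coded as none, the observed risk is p(1 − q). With loss in LAIV4 only, the same enumeration gives 8.7%, 13.7% and 29.3% for q = 5%, 10% and 20%, from a base of 5.3%.

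**5. Sensitivity of one result.** With 16 of 135 events in each arm, the upper bound is 6.5 points. Five further LAIV4 events, had they been recorded, would raise it to 10.6 points, above the margin; four would leave it at 9.8.

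**6. The texts side by side.** Section 4.10 sets a 42-day SAE window for participants in general. Section 7.1 asks for a withdrawn child's data up to withdrawal and is silent on what follows. No text in protocol sections 4.8 to 4.10, 6 or 7, or in the SAP, says which governs a vaccinated child withdrawn without withdrawal of consent.

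**The case against.** Several stronger readings are tempting, and the documents do not support them.

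- **That 7.1 forbids later collection or contradicts 4.10.** It does neither. It asks for effort up to withdrawal and is silent afterwards, and 4.10 could be read to cover withdrawn children. The two are unreconciled, not contradictory.
- **That the plan is biased toward LAIV4.** This needs more loss of event-bound children in LAIV4 than in IIV4. Open label makes that possible, but nothing in the documents shows it, and loss in IIV4 only moves the error rate the other way.
- **That the planned 10% dropout measures the problem.** That figure covers all causes. Consent withdrawal and loss to follow-up are separate grounds that no wording change can recover, and investigator withdrawals over 42 days of mostly remote contact may be few.
- **That later events can never be learned.** Parents are told at Visit 1 to report unscheduled asthma visits and new control medication, and section 6 describes VAERS reporting. These are partial safeguards, not scheduled follow-up.

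Two further objections have weight. A worsening that prompts withdrawal may often already meet the exacerbation definition, and 7.1 keeps data collected before withdrawal; this weakens the mechanism for ITT but not for PP43, which drops the child anyway. Also, continuing the calls alone would not repair PP43, because a child who answers calls but has stopped the diary might still count as not having completed procedures. The fix has to address that.

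What stands is that no text provides for follow-up after an investigator withdrawal, although such a withdrawal ends only observation.

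**Conclusion.** The gap is real and worth closing. Followed as written, sections 7 and 7.1 let a site stop observing a vaccinated child without withdrawal of consent, inside the window that the primary endpoint and the SAE objective are meant to cover. The child then drops out of PP43 and may be coded event-free in ITT.

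The size and direction of any bias are unknown. The figures above are illustrations: they assume true risks exactly at the margin, withdrawal before the event, and chosen loss fractions. Under those assumptions, the chance of a false claim ranges from 1.8% (20% loss in IIV4 only) to 21.1% (20% loss in LAIV4 only), against 5.2% without loss. They show that a handful of children can matter, not that the trial will go wrong. The recommendation rests on the low cost of the change and on the fact that uncollected outcomes cannot be recovered at analysis.

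**What to change.** 1. **Protocol 7.1.** State that, unless the parent withdraws consent or the child cannot be reached, the scheduled contacts for medical services utilization, concomitant medications and SAEs continue through Day 43. This applies after an investigator withdrawal and after a family stops the diary or peak flow.
2. **Use of the data.** State in 7.1 and the SAP that outcomes collected this way enter the ITT and SAE analyses.
3. **PP43 (protocol 8.2, SAP 6.2).** For the primary endpoint, define completion of procedures through Day 43 as exacerbation status ascertained through Day 43. The other PP43 exclusions stay as they are.
4. **Reconcile** protocol sections 4.10, 7 and 7.1 on what is collected for a vaccinated child withdrawn without withdrawal of consent. Leave the investigator's grounds for withdrawal in section 7 unchanged.

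The cost is a wording change in both documents and a few extra calls to less cooperative families, using contacts already in the schedule. Families who withdraw consent or cannot be reached remain lost, and the change does not claim to recover them.

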7.2 Termination of Study

This study may be terminated for safety concerns of the PI, CDC, or participating IRBs.

8 STATISTICAL CONSIDERATIONS

8.1 Sample Size Calculations

This study aims to enroll approximately 300 participants (at least 100 from Vanderbilt, at least 110 from Cincinnati, and at least 90 from Duke). We assume that the proportion of asthma exacerbations in 42 days (until day 43) after vaccination is 12% after LAIV4 and IIV4.⁴ We also assume that ~10% of the children may drop out, yielding a total sample of at least 270 (135 LAIV4 and 135 IIV4).

We expect the proportion of asthma exacerbation in LAIV4 (experimental group) will be at least as high as IIV group (control group). The power estimate is shown below, given delta of 10% and one-sided alpha is set at 5% level.

Proportion of asthma exacerbation in control IIV4 group (pc)	Proportion of asthma exacerbation in LAIV4 experimental group (pe)	Estimated power to reject H0: pe – pc>=10%
12%	12%	81.1%

The null hypothesis will be rejected (and delta margin non-inferiority claimed) when the upper bound of the 95% one-sided confidence interval for the PE-PC is less than 10%. IBM SPSS SamplePower software version 3.0.1 was used for the power calculation which was not adjusted for stratifying by site.

8.2 Analysis plan

Descriptive analyses will be summarized for continuous variables with mean, standard deviation, median, and interquartile range. Categorical variables will be summarized with frequencies and percentages. Explanatory figures will be generated to evaluate the data distribution. Comparisons of demographic characteristics between LAIV4 and IIV4 groups will be conducted using Pearson Chi-square and Wilcoxon tests appropriately.

We will prepare three datasets for analyses populations for main analysis of the primary and secondary objectives. These are defined below.

Intent-to-Treat (ITT) Population:

The ITT Population includes any participant that was enrolled, randomized into the study, and received a study vaccine at Visit 1.

Per Protocol Population for 43 Days:

The Per Protocol Population for 43 days is a subset of the ITT Population. This is defined as all participants who were randomized, vaccinated, completed study procedures through day 43, had no protocol violations that are likely to affect the objectives, and did not receive a second dose of influenza vaccine before day 43.

Per Protocol Population for 15 Days

The Per Protocol Population for 15 days is a subset of the ITT Population. This is defined as all participants who were randomized, vaccinated, completed study procedures through day 15, and have no protocol violations that are likely to affect the objectives.

The Per Protocol population for 43 days is the primary analysis population for the Primary Objective. Statistical analyses for the Primary Objective will be performed for the ITT population and the Per Protocol for 43 days, or the ITT Population only if no participants are excluded from the Per Protocol Population. The Per Protocol population for 15 days is the primary analysis population for the Secondary Objectives. Statistical analyses for the Secondary Objectives will be performed for the ITT population and Per Protocol population for 15 days, or the ITT Population only if no participants are excluded from the Per Protocol Population. The list of major protocol violations for analysis will be provided in the Statistical Analysis Plan (SAP).

In the ITT and Per Protocol populations, participants will be analyzed according to randomization assignment, rather than treatment group. If applicable, sensitivity analyses on primary and secondary objectives will be done on datasets defined by treatment group. For example, if a participant was assigned to LAIV4 and inadvertently received IIV4 that participant would be reassigned to the IIV4 treatment group in the sensitivity analyses.

Adjustments for enrollment site and/or other covariates for study objectives will be described in the comprehensive Statistical Analysis Plan (SAP). The analysis methods for the exploratory objectives, as well as sensitivity analyses, will be also be detailed in the SAP.

All analyses will be performed using R 3.5.0 (r-project.org), SAS version 9.4, or STATA version 15, or updated software from these programs.

